## 1 SYNOPSIS

---

**TITLE:** Phase 3, Randomized, Double-Blind, Placebo-Controlled Trial, with Cross-Over, of Posoleucel (ALVR105) for the Treatment of Adenovirus Infection in Pediatric and Adult Participants Receiving Standard of Care Following Allogeneic Hematopoietic Cell Transplantation

---

**PROTOCOL NUMBER:** P-105-303

---

**INVESTIGATIONAL PRODUCT:** Posoleucel (ALVR105)

---

**PHASE:** 3

---

**RATIONALE:**

During the period of immune recovery after allogeneic hematopoietic cell transplant (allo-HCT), viral infections and reactivations, including those with adenovirus (AdV), are an important cause of morbidity and mortality. One out of 3 children and approximately 6% of adults are reported to have an AdV infection within 6 months post allo-HCT ([Sedláček 2019](#)). Progression to AdV disease is associated with significant morbidity and mortality rates of up to 50% in this population ([Zecca 2019](#)). Preliminary safety and efficacy data of posoleucel for the treatment of opportunistic viral infections common to immunocompromised allo-HCT patients, including AdV, were recently generated from a Phase 2 proof-of-concept study ([Tzannou 2017](#)).

This Phase 3, multicenter, randomized, double-blind, placebo-controlled study will assess the safety and efficacy of posoleucel for the treatment of AdV infection in pediatric and adult allo-HCT recipients receiving standard of care (SoC).

---

**OBJECTIVES AND ENDPOINTS:**

Objectives	Endpoints
Primary Efficacy	

To compare the percent of participants who have clearance of AdV viremia at Day 29 in participants receiving posoleucel and SoC to that in participants receiving placebo and SoC.

 

Proportion of participants with undetectable viremia (less than lower limit of quantitation [LLOQ]) at Day 29.

Primary Safety	

To determine the safety and tolerability of posoleucel by analyzing the incidence and severity of treatment-emergent adverse events (TEAEs), including individual AEs of special interest (AESIs).

 

Incidence and severity of TEAEs, including individual AESIs, during the study.

Key Secondary Efficacy	

 
To determine the percent of participants who develop target organ AdV disease (eg, lower tract respiratory disease documented radiographically, AdV-associated hemorrhagic cystitis, severe hepatitis) or whose target organ disease progresses during the study.
 
	
 
Proportion of participants with disease progression or non-relapse mortality during the study. Progression is defined as: 
 
progression from viremia to target organ disease (for participants without target organ disease at screening), or
 
progression of target organ disease (for participants with target organ disease at screening).
 
 
 


 
To evaluate the effect of posoleucel on AdV viremia over a 28-day period.
 
To determine the percent of participants who develop target organ AdV disease (eg, lower tract respiratory disease documented radiographically, AdV-associated hemorrhagic cystitis, severe hepatitis) or whose target organ disease progresses by Day 29.
 
To determine the percentage of participants who achieve AdV viremia <400 copies/mL AdV DNA.
 
To assess the effect of posoleucel on time to clearance of AdV viremia.
 
	
 
Proportion of participants with undetectable viremia (less than LLOQ) at Day 29 in participants: 
 
without AdV disease at screening.
 
with AdV disease at screening.
 
 
 
Time-averaged area under the concentration-time curve (AAUC) for plasma AdV viremia (<math>\log_{10}</math> copies/mL AdV DNA) as assayed by quantitative polymerase chain reaction (qPCR) through Day 29 for all participants.
 
AAUC for plasma AdV viremia (<math>\log_{10}</math> copies/mL AdV DNA) as assayed by qPCR through Day 29 for participants with no target organ disease at screening.
 
Proportion of participants with disease progression or non-relapse mortality by Day 29. Progression is defined as: 
 
progression from viremia to target organ disease (for participants without target organ disease at screening), or
 
progression of target organ disease (for participants with target organ disease at screening).
 
 
 
Proportion of participants who achieve AdV viremia <400 copies/mL AdV DNA at Day 29.
 
Time to undetectable AdV viremia (less than LLOQ).
 


 
To evaluate the proportion of participants who have recurrence of viremia (<math>\geq 10,000</math> copies/mL AdV DNA) and/or target organ disease during the study (among participants who had clearance of AdV viremia).
 
To evaluate the proportion of participants who are target organ disease-free at Day 29 and at the end of the study.
 
	
 
Proportion of participants with AdV disease recurrence during the study among participants who had clearance of AdV viremia (prior to any cross-over).
 
Proportion of participants who are target organ disease-free at Day 29 and at the end of the study.
 

Exploratory Efficacy and Safety
 
 
To assess length of hospital stay, days spent in the intensive care unit (ICU), hospital re-admission, the need for mechanical ventilation, and the need for supplemental oxygen.
 
	
 
Number of days in the hospital (for any reason including, but not limited to, AdV) during the study.
 
Number of days in the hospital due to AdV-related infection.
 
Number of hospitalizations/re-hospitalizations for any reason during the study.
 
Number of days spent in the ICU during the study.
 
Proportion of participants who need mechanical ventilator support, and number of days ventilator support is required during the study.
 
Proportion of participants who require supplemental oxygen to maintain <math>\text{SpO}_2 >90\%</math>, and number of days supplemental oxygen is required during the study.
 
Persistence of posoleucel cells.
 

 
To evaluate the persistence of posoleucel cells.
 
To determine the viral re-activation and disease occurrence due to BK virus (BKV), cytomegalovirus (CMV), human herpesvirus 6 (HHV-6), Epstein-Barr virus (EBV), or John Cunningham virus (JCV).
 
	
 
Proportion of participants who develop viremia and/or clinical disease (per Investigator assessment) by Day 29 (due to BKV, CMV, HHV-6, EBV, and/or JCV) for those participants without viremia at randomization.
 
Proportion of participants with resolution of viremia by Day 29 (due to BKV, CMV, HHV-6, EBV, and/or JCV) for those participants with viremia at randomization.
 


 
To evaluate non-relapse and all-cause mortality.
 
	
 
Non-relapse mortality at Week 24.
 
All-cause mortality at Week 24.
 
Death due to AdV disease.
 
Proportion of participants with undetectable AdV viral load (less than LLOQ) in a) stool, and b) nasopharyngeal swab at Day 29.
 
Time to undetectable AdV viral load (less than LLOQ) in stool.
 
Proportion of participants with a decrease in AdV viremia of at least <math>2 \log_{10}</math> copies/mL AdV DNA from randomization at Day 29.
 
Comparison of AdV viral load versus progression/non-relapse mortality.
 
Comparison of the rates of progression/non-relapse mortality in those participants who demonstrate AdV viremia clearance versus those who do not.
 
Change in the European Quality of Life 5 dimensions (EQ-5D) at Day 29 and Week 24.
 

 
To determine the percent of participants who have clearance of AdV in a) stool, and b) nasopharyngeal swab at Day 29.
 
To assess the effect of posoleucel on time to resolution of AdV in stool.
 
To determine the percent of participants with a decrease in AdV viremia of at least <math>2 \log_{10}</math> copies/mL AdV DNA from randomization at Day 29.
 
To explore the correlation between magnitude of AdV viremia and progression or non-relapse mortality.
 
To explore the correlation between clearance of AdV viremia and progression or non-relapse mortality.
 
To assess the age-appropriate impact on quality of life.
 
	

1. Non-relapse mortality is defined as death without relapse/recurrence post allo-HCT.

Abbreviations: AAUC = time-averaged area under the concentration-time curve; AdV = adenovirus; AEs = adverse events; AESIs = adverse events of special interest; allo-HCT = allogeneic hematopoietic stem cell transplant; BKV = BK virus; CMV = cytomegalovirus; CRS = cytokine release syndrome; EQ-5D = European Quality of Life 5 dimension; GVHD = graft versus host disease; HHV-6 = human herpesvirus 6; JCV = John Cunningham virus; LLOQ = lower limit of quantitation; qPCR = quantitative polymerase chain reaction; SoC = standard of care.

---

## POPULATION:

### Inclusion Criteria

Patients must meet all of the following criteria in order to be eligible for enrollment into the study. Screening laboratory criteria can be confirmed using local or central laboratories.

1. Male or female of any age.
2. Has undergone allogeneic (including umbilical cord) cell transplantation  $\geq 21$  days prior to dosing and has demonstrated engraftment with an absolute neutrophil count  $>500/\text{mm}^3$ , AND has one of the following:
  - a. AdV viremia DNA  $\geq 10,000$  copies/mL at screening, OR
  - b. Two consecutive and rising AdV viremia DNA results of  $\geq 1,000$  copies/mL at screening, AND
    - i. has absolute lymphocyte count  $<180/\text{mm}^3$ , OR
    - ii. has received T cell depletion, OR
    - iii. had a cord blood transplant.
3. Males and females of childbearing potential who engage in heterosexual intercourse must agree to use contraception as detailed in [Appendix 5](#) of this protocol and refrain from donating sperm or eggs for at least 90 days after treatment completion.
4. Willing and able to provide signed informed consent.
5. Has an HLA type matching with at least 1 suitably matched and available posoleucel VST line for infusion.

### Exclusion Criteria

Patients who meet any of the following criteria will be excluded from participation in the study:

1. Grade 3 or higher acute GVHD (see [Appendix 6](#) for information on acute GVHD grading and severity).
2. Ongoing therapy with high-dose systemic corticosteroids (ie, prednisone dose  $>0.5 \text{ mg/kg/day}$  or equivalent). Patients actively undergoing corticosteroid tapering during Screening may randomize and dose once they have reached  $\leq 1.0 \text{ mg/kg/day}$  with Medical Monitor approval, with the expectation that the corticosteroid taper will continue.
3. Has either of the following laboratory parameters at screening:
  - a. Aspartate aminotransferase and alanine aminotransferase serum levels  $\geq 5$  times the upper limit of normal (ULN), OR
  - b. Direct bilirubin serum levels  $\geq 3$  times the ULN.

Exception: Patients with elevations of these laboratory parameters may be included if these elevations are attributed to AdV hepatitis and are not considered attributable to other etiologies.

---

---

4. Relapse of primary malignancy, or any other active malignancy, except for non-melanoma skin cancer. Malignancies that are slow growing and/or stable may be allowed with Medical Monitor approval.
5. Grade 4 diarrhea (ie, life-threatening consequences with urgent intervention indicated) regardless of attribution ongoing or within 7 days prior to randomization.
6. Uncontrolled viral (other than AdV), bacterial, or fungal infection(s) leading to hemodynamic instability or radiologic or laboratory evidence attributable to worsening disease.
7. Requirement for fraction of inspired oxygen (FiO2) >0.5 (ie, 50%) to maintain arterial oxygen saturation >90% (via pulse oximetry) or need for mechanical ventilation, except for planned procedures or surgeries with Medical Monitor approval. For guidance on estimating fraction of inspired oxygen, see [Appendix 9](#).
8. Prior therapy with anti-thymocyte globulin, alemtuzumab (Campath®), or other immunosuppressive T cell monoclonal antibodies within 28 days prior to dosing.
9. Prior donor lymphocyte infusion or CD34+ stem cell infusion within 21 days prior to dosing.
10. Use of vasopressors within 7 days prior to randomization.
11. Use of any investigational antiviral agent, including brincidofovir, within 7 days prior to randomization. Maribavir and letermovir for CMV will be allowed.
12. Pregnant or lactating female unwilling to discontinue nursing prior to randomization.
13. Any condition that, in the opinion of the Investigator, would compromise the safety of the patient, would prevent full participation in this study, or would interfere with the evaluation of any study endpoints.
14. History of severe (Common Terminology Criteria for Adverse Events [CTCAE] Grade  $\geq 3$ ) allergy to any component of posoleucel (including human serum albumin and dimethyl sulfoxide) or history of severe (CTCAE Grade  $\geq 3$ ) prior reactions to blood product transfusions.
15. Positive for SARS-CoV-2 virus at screening.  
Exception: Patients who test positive for SARS-CoV-2 at screening and who have a recent prior positive test may be enrolled if they have no clinical or radiological manifestations of COVID-19 and if the Investigator and Medical Monitor concur on their enrollment.

---

## STUDY DESIGN AND DURATION:

This is a Phase 3, multicenter, randomized, double-blind, placebo-controlled study to assess the safety and efficacy of posoleucel as compared to placebo for the treatment of AdV infection in pediatric and adult recipients of HCT with AdV infections receiving SoC.

Approximately 82 eligible patients may be randomized [ ] to receive [ ] sequential infusions of posoleucel or placebo (separated by [ ]). Randomization will be stratified [ ]

---

[REDACTED]  
[REDACTED]

The presence or absence of adenovirus target organ disease at screening will be determined initially by the Investigator (using the criteria in [Appendix 8](#)) and reviewed subsequently by the Adjudication Committee for analysis purposes.

The Primary Study Period is 4 weeks (28 days) for evaluation of efficacy, including the primary endpoint, plus 20 weeks for safety follow-up, for a total study duration of 24 weeks. For participants who cross-over, the Cross-Over Period is 4 weeks (28 days), plus 20 weeks for safety follow-up. Participants who experience recurrence and receive an additional dose will have safety follow-up for 20 weeks after the final dose.

At Day 29, all participants will be assessed for the primary endpoint, virologic response.

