## 5 STUDY DESIGN

### 5.1 Overall Design

This is a Phase 3, multicenter, randomized, double-blind, placebo-controlled study to assess the safety and efficacy of posoleucel as compared to placebo for the treatment of AdV infection in pediatric and adult recipients of HCT with AdV infections receiving SoC.

Approximately 82 participants at approximately 50 clinical sites in the US, Europe, and Canada who meet all of the inclusion criteria and none of the exclusion criteria may be enrolled into the study and randomized █ to receive posoleucel or placebo. Randomization will be stratified █

█ It is expected that no more than 30% of participants, but at least 10% of participants, will be  $\geq 18$  years of age.

Enrollment of participants  $<1$  year of age will occur once preliminary safety data are available from 5 participants  $\geq 1$  and  $\leq 6$  years of age. On 16May2023, the DSMB reviewed data from 6 participants aged 1-6 years that have completed through D29 and recommended opening enrollment to patients  $<1$  year of age. An additional meeting will be held once 6 patients  $<1$  year old have been enrolled and completed through D29 of the study.

Posoleucel is to be administered at a fixed cell dose based on weight, as █ sequential infusions separated by █ (see [Section 7.1](#)).

The Primary Study Period is 4 weeks (28 days) for evaluation of efficacy, including the primary endpoint, plus 20 weeks for safety follow-up, for a total study duration of 24 weeks. For participants who cross over, the Cross-Over Period is 4 weeks (28 days), plus 20 weeks for safety follow-up. Participants who experience recurrence and receive an additional dose will have safety follow-up for 20 weeks after the additional dose of study treatment.

At Day 29, all participants will be assessed for the primary endpoint, virologic response.

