**5.2 Participant and Study Completion**

Approximately 115 participants will be screened to achieve 82 randomly assigned to study treatment and dosed to obtain an estimated total of 41 participants per treatment group evaluable for the primary endpoint.

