## **8.2 Withdrawal from the Study**

Participation in this clinical study may be discontinued for any of the following reasons:

- The participant (or parent or legal guardian) withdraws consent.
- The participant (or parent or legal guardian) requests discontinuation from the study for any reason.
- Participant failure to comply with protocol requirements or study-related procedures.
- Termination of the study by the Sponsor or the regulatory authority.

If a participant withdraws prematurely from the study due to the above criteria or any other reason, study staff should make every effort to complete an Early Termination Visit (see the SoA in [Section 2](#)). The reason for participant withdrawal must be documented in the eCRF.

Withdrawn participants will not be replaced.

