## 10 STATISTICAL CONSIDERATIONS

### 10.1 Sample Size Determination

The required sample size is 82 participants based on the below specifications that have received at least 1 dose of posoleucel or PBO.

The sample size was determined based on the following specifications:

1. Superiority study comparing posoleucel plus SoC to placebo plus SoC
2. Primary endpoint is success or failure based on clearance of ADV viremia at Day 29 of the Primary Study Period
3. Allocation (posoleucel:placebo) is █
4. Chi-square test
5. Two-sided alpha = 0.05
6. True success rate (defined as clearance of virus) for posoleucel = 0.55
7. True success rate (defined as clearance of virus) for placebo = 0.25
8. Power = 80%

A SSRE and futility analysis will be performed after approximately 40 participants have completed Day 29 of the Primary Study Period. Details of the SSRE and futility analysis will be provided in the SSRE Plan prior to conducting the interim analyses.

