### **Change from ITT to mITT**

**Rationale:** The time from randomization to study treatment infusion is typically delayed by ~5 days due to operational feasibility of shipping HLA matched VST or placebo to the study center and scheduling of treatment administration. This delay has led to a larger than expected number of patients that have randomized and not been treated. Given the smaller sample size in this rare patient population study, an ITT analysis that includes randomized but not treated patients has the potential to obscure the biological effects of VST versus placebo for the primary endpoint. Excluding randomized patients who did not receive at least 1 infusion of study treatment (ie. modified ITT analysis) is not expected to introduce bias by performing the primary analysis on a post-randomization population. The reason patients were randomized and not treated was not influenced by treatment assignment as the study is blinded. The primary reasons for patient not to receive treatment are withdraw of consent from study or new data becoming available after randomization and prior to treatment that can lead to removal of the patient from the study, including clearance of AdV viremia. Excluding these patients will lead to a more informative analysis focused only on patients that received at least 1 dose of study treatment.

The mITT analysis would better represent the treatment response in real-world clinical practice in which patients that clear AdV viremia or decide against treatment would not receive VSTs. The primary efficacy endpoints will also be analyzed based on the ITT Population to assess the robustness of the primary analysis results.

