2.2 Study Design

2.2.1 *Overview*

This is a Phase 3, multicenter, randomized, double-blind, placebo-controlled study to assess the safety and efficacy of posoleucel as compared to placebo for the treatment of AdV infection in pediatric and adult recipients of HCT with AdV infections receiving SoC.

Approximately 80 participants may be randomized [] to receive [] infusions of posoleucel or placebo []). Randomization will be stratified []

It is expected that no more than 30% of participants, but at least 10% of participants, will be []. Enrollment of participants <1 year of age will occur once preliminary safety data are available from 5 participants ≥ 1 and ≤ 6 years of age. The Data Safety Monitoring Board (DSMB) will review data through Day 29 from these 5 participants once available and make a recommendation. A formal memo will be provided to ethics committees and sites once the DSMB approves enrollment of participants <1 year of age.

The Primary Study Period is 4 weeks (28 days) for evaluation of efficacy, including the primary endpoint, plus 20 weeks for safety follow-up, for a total study duration of 24 weeks. For participants who cross over, the Cross-Over Period is 4 weeks (28 days), plus 20 weeks for safety

[figure not shown]
follow-up. Participants who experience recurrence and receive an additional dose will have safety follow-up for 20 weeks after the final dose.

Participants who progress to active target organ disease or whose existing target organ disease progresses (as assessed by the Investigator and Sponsor Medical Monitor and based on the criteria in Appendix 8 of the protocol) between Day 29 and Week 10 will be considered to have experienced progression and will have the option to be crossed over to the alternate treatment arm. Participants can cross over before Day 29 only if they progress with target organ disease as adjudicated by the Adjudication Committee. Cross-over participants will receive the alternate treatment to which they were originally randomized, posoleucel or placebo [redacted] sequential infusions separated by [redacted] \pm 3 days), but study treatment will remain blinded.

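### The sample size needs 82 dosed participants, but the synopsis and Section 5.1 plan about 82 randomized and the SAP about 80; the counts should be reconciled, because stopping at those numbers would leave power below 80% if undosed participants are excluded

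*Protocol*

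**What the plan says.** Two kinds of count appear.

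**Number randomized.**
- Protocol synopsis, study design and duration: "Approximately 82 eligible patients may be randomized".
- Protocol Section 5.1: "Approximately 82 participants at approximately 50 clinical sites in the US, Europe, and Canada" may be enrolled and randomized.
- SAP Section 2.2.1: "Approximately 80 participants may be randomized".

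**Number dosed.**
- Protocol Section 10.1: "The required sample size is 82 participants based on the below specifications that have received at least 1 dose of posoleucel or PBO". The synopsis sample size section and SAP Section 2.2.4 make the same statement.
- Protocol Section 5.2: about 115 are screened to reach "82 randomly assigned to study treatment and dosed to obtain an estimated total of 41 participants per treatment group" evaluable for the primary endpoint.

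The primary efficacy population is the mITT set, that is, randomized participants who received at least one dose (Protocol Section 10.2, SAP Section 3.2.2). In Protocol Appendix 10, the rationale for changing from ITT to mITT describes a gap of about five days between randomization and infusion and reports: "This delay has led to a larger than expected number of patients that have randomized and not been treated". It gives no rate. Section 8.2 adds: "Withdrawn participants will not be replaced".

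**The concern.** The number randomized equals the number dosed only if nobody goes undosed, and the protocol says that this has not been so. The mITT definition then removes the undosed from the primary analysis. The Amendment 4 rationale explains why no dropout inflation was applied: people who drop out stay in the analysis. That argument covers participants lost after dosing. It does not cover those who are never dosed.

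The documents therefore state a requirement of 82 dosed, a plan of about 82 or 80 randomized, and no number to randomize in order to obtain 82 dosed. Whoever manages enrolment cannot tell from the synopsis, Section 5.1 or the SAP whether to stop at 82 randomized or at 82 dosed. At stake is the 80% power on which the sample size rests. There is little slack in it.

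**Working it through.** **Inputs.** Success rates 0.55 (posoleucel) and 0.25 (placebo), chi-square test, two-sided alpha 0.05 and power 80% are from Protocol Section 10.1. The 1:1 allocation is from the synopsis sample size section. The one-sided 0.025 test in Section 10.3.1.1 is equivalent for power in the expected direction.

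**Reproducing the plan's figure.** With pooled variance and no continuity correction, the number per arm is

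n = [z₀.₉₇₅ √(2 p̄ q̄) + z₀.₈₀ √(p₁q₁ + p₂q₂)]² / (p₁ − p₂)²

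- p̄ = 0.40, so √(2 × 0.40 × 0.60) = 0.6928
- √(0.55 × 0.45 + 0.25 × 0.75) = √0.435 = 0.6595
- n = (1.960 × 0.6928 + 0.8416 × 0.6595)² / 0.30² = (1.913)² / 0.09 = 40.7, rounded up to 41

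This gives 41 per arm and 82 in total, as stated.

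**Power at a given number dosed.** With n per arm,

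power = Φ{ [0.30 √n − 1.960 × 0.6928] / 0.6595 }

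For n = 41: (1.921 − 1.358) / 0.6595 = 0.854, so power is 80.3%. For n = 40: (1.897 − 1.358) / 0.6595 = 0.818, so power is 79.3%.

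**If randomization stopped at the stated count.** The documents give no undosed rate, so a range of 0% to 20% is assumed and taken as equal in both arms. Dosed N is the randomized count times (1 − undosed rate), and n is half of that.

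| Undosed (assumed) | 82 randomized: dosed | Power | 80 randomized: dosed | Power |
|---|---|---|---|---|
| 0% | 82 | 80.3% | 80 | 79.3% |
| 5% | 77.9 | 78.2% | 76 | 77.2% |
| 10% | 73.8 | 75.9% | 72 | 74.9% |
| 15% | 69.7 | 73.4% | 68 | 72.4% |
| 20% | 65.6 | 70.8% | 64 | 69.6% |

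**Check on the approximation.** Exact binomial power of the uncorrected chi-square test is 81.7% for 82 dosed, 80.2% for 80, 78.8% for 78, 75.5% for 74 and 74.0% for 66. The direction is the same. Because the outcomes are discrete, the exact figures do not fall smoothly, and the loss at 66 dosed is smaller than the formula suggests. On the exact calculation, 80 dosed still reaches 80%.

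**Number to randomize for 82 dosed.** 82 / (1 − u), rounded up, is 87 at 5% undosed, 92 at 10%, 97 at 15% and 103 at 20%.

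**The case against.** The strongest answer is Section 5.2, which expressly sets the target as 82 randomized and dosed, with 41 evaluable per group. It agrees with Section 10.1, and under it the stated power is delivered. A reader might infer from the synopsis and Section 5.1 that the trial could not reach its stated power. The documents do not support that. This part of the objection stands, and Section 5.2 needs no correction.

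It is also fair that the overview sentences say approximately and may. They set no hard stop, and none says that randomization ends at 82 or 80. The rule against replacing withdrawn participants does not prove a shortfall either: leaving an individual unreplaced is compatible with randomizing until 82 are dosed.

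The sample size re-estimation after about 40 participants complete Day 29 could raise N. It responds to interim conditional power, however, and is not a planned allowance for undosed participants. It makes 82 provisional without settling what the 82 counts.

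The size of any loss rests on an assumed rate. The protocol's remark about undosed participants is qualitative. At 5% undosed the shortfall is about 2 points, and the SAP's 80 in place of 82 costs about 1 point by itself.

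Lastly, the SAP states that the trial was terminated for futility and that no hypothesis tests will be done. A wrong count there affects no result.

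The mismatch remains after all of this: three statements attach the count to randomization, while the sample size requirement attaches it to dosing.

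**Conclusion.** The concern holds as an inconsistency with a conditional effect on power. The requirement of 82 dosed is correctly calculated (80.3% power). The synopsis, Section 5.1 and SAP Section 2.2.1 do not match it, given that some randomized participants go undosed and are left out of the primary analysis.

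If randomization stopped at 82, power would be about 78% with 5% undosed, 76% with 10% and 71% with 20%. If it stopped at 80 and all were dosed, power would be 79.3%. These figures assume 0.55 versus 0.25, the pooled-variance formula, equal undosed rates in the two arms and no increase from the re-estimation. If Section 5.2 governs, nothing is lost. The documents do not establish that the stated power is missed, and they do not support any particular reduced figure.

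The SAP's posoleucel rate of 0.50, against the protocol's 0.55, is a separate and larger discrepancy: at 0.50 versus 0.25 the same formula needs 116 participants, and 82 gives 65.2%. Correcting the 80 would not resolve it.

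**What to change.** Align the Protocol synopsis, Protocol Section 5.1 and SAP Section 2.2.1 with Protocol Sections 5.2 and 10.1 by stating that randomization continues until 82 participants have received at least one dose. Giving the expected number to randomize, with the undosed rate behind it, would help. Replace the SAP's 80 accordingly.

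If the sponsor means to stop at 82 randomized, say so and restate the power for the number expected to be dosed, using an undosed rate taken from the trial's blinded data. The illustrative rates above should not be written into the plan.

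The first option costs only wording in the documents; in an ongoing trial it would mean randomizing somewhat more than 82. The second costs a less favourable power statement. For the terminated trial's abbreviated SAP, either change corrects the stated design figure and leaves every analysis as it is.
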